9.4 Pregnancy reporting

To ensure patient safety, each pregnancy in a patient on study drug must be reported to Novartis within 24 hours of learning of its occurrence. The pregnancy should be followed up to determine outcome, including spontaneous or voluntary termination, details of the birth, and the presence or absence of any birth defects, congenital abnormalities, or maternal and/or newborn complications. The study drug must be discontinued, though the patient may stay in the study, if she wishes to do so. All assessments that are considered as a risk during pregnancy must not be performed. The patient may continue all other protocol assessments. Pregnancy must be recorded on a Pharmacovigilance Pregnancy Form and reported by the investigator to the local Novartis Drug Safety and Epidemiology Department. Pregnancy follow-up should be recorded on the same form and should include an assessment of the possible relationship to the Novartis study drug of any pregnancy outcome. Any SAE experienced during pregnancy must be reported on an SAE Report Form.

Pregnancy outcomes must be collected for the female partners of any males who took study treatment in this study. Consent to report information regarding these pregnancy outcomes should be obtained from the mother.

9.5 Early phase safety monitoring

The Investigator will monitor adverse events in an ongoing manner and inform the Sponsor of any clinically relevant observations. Any required safety reviews will be made jointly between medically qualified personnel representing the Sponsor and Investigator. Such evaluations may occur verbally, but the outcome and key discussion points will be summarized in writing (e-mail) and made available to both Sponsor and all Investigator(s). Criteria pertaining to stopping the study/treatment or adapting the study design are presented above.

When two or more clinical site(s) are participating in the clinical study, the Sponsor will advise the Investigator(s) at all sites in writing (e-mail) (and by telephone if possible) of any new, clinically relevant safety information reported from another site during the conduct of the study in a timely manner.

10 Data review and database management

10.1 Site monitoring

Before study initiation, at a site initiation visit or at an investigator's meeting, a Novartis representative will review the protocol and CRFs with the investigators and their staff. During the study Novartis employs several methods of ensuring protocol and GCP compliance and the quality/integrity of the sites' data. The monitor will visit the site to check the completeness of patient records, the accuracy of entries on the CRFs, the adherence to the protocol and to Good Clinical Practice, the progress of enrollment, and to ensure that study drug is being stored, dispensed, and accounted for according to specifications. Key study personnel must be available to assist the monitor during these visits.

The investigator must maintain source documents for each patient in the study, consisting of case and visit notes (hospital or clinic medical records) containing demographic and medical information, laboratory data, electrocardiograms, and the results of any other tests or assessments. All information on CRFs must be traceable to these source documents in the patient's file. The investigator must also keep the original informed consent form signed by the subject (a signed copy is given to the subject).

The investigator must give the monitor access to all relevant source documents to confirm their consistency with the CRF entries. Novartis monitoring standards require full verification for the presence of informed consent, adherence to the eligibility criteria, documentation of SAEs, and the recording of data that will be used for all primary and safety variables. Additional checks of the consistency of the source data with the CRFs are performed according to the study-specific monitoring plan. No information in source documents about the identity of the patients will be disclosed.

10.2 Data collection

Designated investigator staff will enter the data required by the protocol into the Electronic Case Report Forms using fully validated software that conforms to 21 CFR Part 11 requirements. Designated investigator site staff will not be given access to the EDC system until they have been trained. Automatic validation programs check for data discrepancies and, by generating appropriate error messages, allow the data to be confirmed or corrected before transfer of the data to the CRO working on behalf of Novartis. The Investigator must certify that the data entered into the Electronic Case Report Forms are complete and accurate. After database lock, the investigator will receive a CD-ROM or paper copies of the patient data for archiving at the investigational site.

Data not requiring a separate written record will be defined in the Site Operations Manual and assessment schedule and can be recorded directly on the CRFs. All other data captured for this study will have an external originating source (either written or electronic) with the CRF not being considered as source.

10.3 Database management and quality control

All data should be recorded, handled and stored in a way that allows its accurate reporting, interpretation and verification.

CRO working on behalf of Novartis review the data entered into the eCRFs by investigational staff for completeness and accuracy and instruct the site personnel to make any required corrections or additions. Queries are sent to the investigational site using an electronic data query. Designated investigator site staff is required to respond to the query and confirm or correct the data. If the electronic query system is not used, a paper Data Query Form will be faxed to the site. Site personnel will complete and sign the faxed copy and fax it back to CRO working on behalf of Novartis who will make the correction to the database.

Concomitant medications entered into the database will be coded using the WHO Drug Reference List, which employs the Anatomical Therapeutic Chemical classification system. Medical history/current medical conditions and adverse events will be coded using the Medical dictionary for regulatory activities (MedDRA) terminology.

Laboratory samples will be processed centrally and the results will be sent electronically to a designated CRO.

Diary data will be entered into an electronic diary by the patient. The system will be supplied by a vendor(s), who will also manage the database. The data will be sent electronically to a designated CRO. In case the electronic diary is not used then the patients will enter data in paper diary. These diaries will be handed over to site and site personnel will enter data in the clinical database or send them to the designated CRO to enter data in the clinical database.

At the conclusion of a non-IRT study, the occurrence of any emergency code breaks will be determined after return of all code break reports and unused drug supplies to Novartis.

The occurrence of any protocol deviations will be determined. After these actions have been completed and the database has been declared to be complete and accurate, it will be locked and the treatment codes will be unblinded and made available for data analysis. Any changes to the database after that time can only be made by joint written agreement between the Global Head of Clinical Information Sciences and the Clinical Franchise Head.

DNA samples:

To maximize confidentiality, all samples and the information associated with the samples will be double-coded to prevent the exposure of the patient's information and identity. This double-coding process allows Novartis to go back and destroy the sample at the patient's request. In addition, sample information is stored in one secured database while genetic data is stored in an independent secured database.

The use of DNA to search for biomarkers of disease and drug action is exploratory. Any results from this DNA study will not be placed in the patient's medical records.

10.4 Data Monitoring Committee

A Data Monitoring Committee (DMC) has been assembled for this compound to monitor safety data. This committee is comprised of Novartis personnel not directly involved with the study and include one or more Novartis physician with expertise in the indication. The DMC will convene as outlined in the DMC Charter to review an event or combination of events that fulfil the study stopping rules defined in [Section 7.4](#).

In addition, adverse events, including clinical laboratory data will be continuously reviewed by the Novartis Clinical trial team, including the study physician, on an ongoing basis as data become available from the Electronic Data Capture system.

10.5 Adjudication Committee

Not required.

11 Data analysis

11.1 Analysis sets

For all analysis sets, patients will be analyzed according to the study treatment(s) received.

The safety analysis set will include all patients that received any study drug.

The PK analysis set will include all patients with available PK data and no protocol deviations with relevant impact on PK data.

The PD analysis set will include all patients with available PD data and no protocol deviations with relevant impact on PD data.

11.2 Subject demographics and other baseline characteristics

All data for background and demographic variables will be listed by treatment sequence (drug followed by placebo or vice-versa) and patient. Summary statistics will be provided for all patients, as well as for each treatment sequence.

Relevant medical history, current medical conditions, results of laboratory screens, drug tests and any other relevant information will be listed by treatment sequence and patient.

11.3 Treatments (study drug, rescue medication, other concomitant therapies, compliance)

Data for study drug administration (rescue medication) and concomitant therapies will be listed by treatment sequence and patient.

11.4 Analysis of the primary variable(s)

11.4.1 Variable(s)

The primary analysis variables are: a) stool frequency, b) and stool form assessed by the Bristol stool chart.

11.4.2 Statistical model, hypothesis, and method of analysis

A repeated measures analysis will be done for the two-dimensional endpoint: weekly stool frequency and the corresponding average stool form. The analysis will include fixed effects for sequence (Drug/Placebo or Placebo/Drug), Treatment (Week 1 Drug, Week 2 Drug, Week 1 Placebo or Week 2 Placebo), and period (1 or 2). The model will assume an arbitrary 2 by 2 covariance matrix for the two-dimensional endpoint (frequency, form) and a compound symmetry covariance matrix for each individual endpoint. Point estimates of the weekly & biweekly treatment effect on stool frequency and form will be reported together with 95% simultaneous confidence intervals (confidence ellipsoids).

Baseline weekly stool frequency and the corresponding average stool form will be analyzed similarly using the method described above to assess unequal carryover effects.

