3.1 Study design

This is a multi-center, double blind (patient and investigator blind, sponsor open label), randomized placebo controlled, crossover study to assess safety, tolerability and efficacy of LJN452 in patients with primary bile acid diarrhea (pBAD). In this study approximately 30 patients will be enrolled to have 24 completers.

This is a non-confirmatory trial.

Each patient will undergo a screening period (28 days), run-in period (washing out previous treatment effect) (up to 14 days), 2 treatment periods (14 days each), washout period (at least 7 up to 28 days) between the treatment periods and end of study.

Figure 3-1 Study design schematic

Patients will be assessed for eligibility to enter the study at the screening visit.

Each patient will perform following visits

Screening visit: Day -28 to -2

During the screening period all patients will undergo screening assessment, which may be completed over multiple visits as per the patient's convenience. The screening results will be valid for 28 days, if any patient is beyond the screening validity, the patient can be re-screened. Results for all screening assessment must be available before the baseline/Day 1 pre-dose assessment.

If the eligibility is confirmed patients will be asked to discontinue their sequestrants. Patients will be handed over patient diary to record their daily stool type and frequency using Bristol Stool Chart and use of rescue medication (loperamide intake). The patient diary is expected to be used by patients' throughout the study duration.

Rescue medication will be loperamide only and patients will be instructed to take 2 mg dose only after passage of 4 stools of Bristol Stool Scale Type 6 (Fluffy pieces with ragged edges, a mushy stool) or Type 7 (Watery, no solid pieces, entirely liquid). This dose may be repeated only after 4 hours have elapsed or passage of 4 further stools of Type 6 or 7 (whichever occurs first). A total of no more than 16mg of loperamide may be taken in a 24 hour period. No BA sequestrants should be used by the patients during this study.

Run-in period (Day -7 to -1 or Day -14 to -1)

Patients who have not used bile acid sequestrants for pBAD in the previous week at the time of screening will be evaluated for inclusion/exclusion criteria during the screening visit, and if found eligible will enter a 1 week run in period (Day -7 to -1) prior to the double blind randomized treatment phase.

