Eligible patients who are treated with bile acid sequestrants (at least one dose during the previous two weeks) will be asked to stop their medication and enter the 2 weeks run-in period (Day -14 to -1) of the study. Patients will be allowed to take rescue medication (loperamide), which will be recorded as concomitant medication.

Patients will continue to use patient diary to record stool type and frequency along with use of rescue medication.

Results for all screening assessment must be available before the baseline/Day 1 pre-dose assessment. Screening and run-in visits may be combined for logistic reasons.

After the run-in period, patients will enter the double blind randomized treatment phase.

There will not be a separate baseline visit, but pre-dose assessment on Day 1 will be considered as baseline assessment.

Treatment Periods (Day 1-14):

On Day 1, patient will handover stool sample collected before dosing as pre-dose stool sample. Pre-dose PK, PD and biomarker samples will be collected before dosing.

In treatment period 1 on Day 1 patients will receive either 60 µg LJN452 or placebo orally once daily for 14 days in a 1:1 ratio. Pharmacokinetic (PK), pharmacodynamic (PD) and safety samples will be collected on Day 1 for up to 8 hours post dose and on Day 2 pre -dose, which corresponds to 24 h after Day 1 dosing. Some PK and PD sample time points on Day 1 and Day 2 can be optional, see [Assessment Schedule](#).

Patients will be handed over trial medication, to be administered at home enough to cover dosing for 14 days in each period. Throughout the 14 days of the treatment period, patients will be directed to take study drug at home with water in the morning in a fasting state, 2 hours prior to the first meal of the day, preferably at the same time of the day.

Following dosing, patients will return to clinic for PK, PD, BM and safety assessment at various time points as described in the [Assessment Schedule](#).

The patients will return to the clinic for a series of PK, PD and biomarker sample collections on Day 12.

After 2 weeks of treatment with LJN452 or placebo, patients will undergo a washout of at least 7 days, up to a maximum of 28 days. At the end of washout period, patients will return to the study site for period 2 of the study. Period 2 will be identical to period 1 except that the treatments will be crossed over.

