6.2 Treatment arms

Patients will be assigned to the 2 treatment sequence (Drug/Placebo or Placebo/Drug) in a ratio of 1:1. The number of patients enrolled may change based on data from interim analyses.

Study treatments are defined as:

- A: Single oral dose of LJN452 60 µg daily for 14 days (administered as LJN452 6 x 10 µg capsules).
- B: Single oral dose of placebo to LJN452 0 µg daily for 14 days (administered as placebo to LJN452 6 x 0 µg capsules).

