6.1.3 Statistical model, assumptions and hypotheses

A repeated measures analysis will be done for the two-dimensional endpoint: weekly stool frequency and the corresponding average stool form. The analysis will include fixed effects for sequence (Drug/Placebo or Placebo/Drug), Treatment (Week 1 drug, Week 2 drug, Week 1 placebo or Week 2 Placebo), and period (1 or 2). The model will assume an arbitrary 2 by 2 covariance matrix for the two-dimensional endpoint (frequency, form) and a compound symmetry covariance matrix for each individual end point. Point estimates of the weekly & biweekly treatment effect on stool frequency and the corresponding average stool form will be reported together with 95% simultaneous confidence intervals (confidence ellipsoids).

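### Compound symmetry in the primary crossover model makes the interval for the two-week drug effect too narrow if weeks of the same period correlate more than weeks of different periods.

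*Protocol*

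**What the plan says.** Protocol 11.4.2 and SAP 6.1.3 describe the same primary efficacy model. The outcome is bivariate: weekly stool frequency and the matching average stool form. The fixed effects are sequence, period and a four-level treatment factor (weeks 1 and 2 on drug, weeks 1 and 2 on placebo). The covariance is an arbitrary 2 by 2 matrix between the two endpoints and, over time, "a compound symmetry covariance matrix for each individual endpoint" (the SAP has "a compound symmetry covariance matrix for each individual end point"). Weekly and two-week treatment effects are to be reported with 95% confidence ellipsoids.

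Neither section names the block to which compound symmetry applies. Neither lists a patient-by-period effect, a robust variance, a degrees-of-freedom method or a sensitivity analysis of the covariance. Protocol 3.2 bases the choice of a crossover on comparing treatments within patient.

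On timing, Protocol 3.1 has two 14-day periods, between which "patients will undergo a washout of at least 7 days, up to a maximum of 28 days". On size, "In this study approximately 30 patients will be enrolled to have 24 completers".

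**The concern.** The natural reading is one block per patient, with one common correlation for all pairs among the four weeks. Such a model cannot let two weeks of the same period correlate more strongly than two weeks of different periods.

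The design suggests that they do. Measured midpoint to midpoint, the two weeks of a period are 1 week apart and on the same treatment. Weeks of different periods are 2 to 4 weeks apart with a 7-day washout, 5 to 7 weeks apart with a 28-day washout, and always on different treatments. Serial correlation is not the only route. If patients differ in how they respond to the drug, their two drug weeks share that deviation and their placebo weeks do not.

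The two-week effect with its joint region is the inferential output for the primary efficacy objective, and Protocol 1.2 says the study is to guide decisions on further development. A region that is too small would make the result look more precise than it is.

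**Working it through.** **Inputs.** There is no figure of the plan to reproduce: the sample size section is redacted and the visible text gives no SD or correlation. From the documents: four weekly values per patient and endpoint, 24 completers, and 1:1 allocation to sequences (taken as 12 + 12). Assumed: the within-period correlation rw, the between-period correlation rb, equal variances (set to 1), complete data, and a correlation of 0.4 between endpoints in the simulations.

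**True variance.** Split the variance into a patient part rb, a patient-by-period part t = rw − rb, and a residual e = 1 − rw. The drug-minus-placebo difference of two-week means has per-patient variance 2t + e = 1 + rw − 2rb. The estimated effect has variance (2t + e)/n.

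**Variance used by compound symmetry.** Of the six pairs of weeks, two are within a period and four between, so in large samples the fitted correlation is about (rw + 2rb)/3. The model then uses 1 − (rw + 2rb)/3 in place of 1 + rw − 2rb. True minus model is (4/3)(rw − rb), which is positive whenever rw > rb.

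**Finite sample, n = 24.** Within-patient df are 24 × 3 − 4 = 68. Of these, 24 − 2 = 22 carry the period contrast and 48 − 2 = 46 carry the week contrasts. Compound symmetry pools them:

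m = [22(2t + e) + 46e]/68

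and uses m/n. At 0.70/0.60, t = 0.10 and e = 0.30, so the true value is 0.50 and m = (11.0 + 13.8)/68 = 0.365. The variance ratio is 0.50/0.365 = 1.37, and the SE ratio is √(0.365/0.50) = 0.85, that is, 15% too small.

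| rw/rb (assumed) | True 2t + e | Model m | Variance ratio | SE of two-week effect | Coverage of 95% ellipsoid, pooled 68 df | Coverage, REML fit |
|---|---|---|---|---|---|---|
| 0.50/0.60 | 0.30 | 0.435 | 0.69 | 20% too large | 98.7% | 98.6% |
| 0.60/0.60 | 0.40 | 0.400 | 1.00 | correct | 95.2% | 94.9% |
| 0.62/0.60 | 0.42 | 0.393 | 1.07 | 3% too small | 93.9% | 94.0% |
| 0.65/0.60 | 0.45 | 0.382 | 1.18 | 8% too small | 92.4% | 92.0% |
| 0.70/0.60 | 0.50 | 0.365 | 1.37 | 15% too small | 88.8% | 88.4% |
| 0.80/0.60 | 0.60 | 0.329 | 1.82 | 26% too small | 80.4% | 80.2% |
| 0.80/0.50 | 0.80 | 0.394 | 2.03 | 30% too small | 77.2% | 76.9% |

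The pooled column rests on 8,000 simulated trials per row. The REML column fits an unstructured endpoint matrix crossed with compound symmetry. A bivariate analysis of patient period means, with Hotelling's T² on 22 df, covered 94.7 to 95.2% in every row.

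**Single-week effects.** The true per-patient variance is 2(1 − rb) and the model uses 2m. In the last four rows the SE is 2%, 5%, 9% and 11% too small.

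**Serial correlation alone.** Weeks were placed at 0, 1, 3, 4 (7-day washout) or 0, 1, 6, 7 (28-day washout), with a patient share of 0.4 to 0.5, a serial share of 0.2 to 0.4 and a weekly autocorrelation of 0.5 to 0.7 (6,000 trials per case). Coverage was 88.2 to 91.6% with the short washout and 83.2 to 90.5% with the long one. Period means gave 94.8 to 95.4%.

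**Other reading of the block.** If compound symmetry applies within each patient-period and there is no patient effect, the two periods are treated as independent and the variance is (1 + rw)/n. At 0.70/0.50 that gives an SE of √(1.70/24) = 0.266, against a true √(0.70/24) = 0.171. The interval is then too wide.

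**Thirty completers.** The df become 28 + 58 = 86. At 0.70/0.60, m = (28 × 0.50 + 58 × 0.30)/86 = 0.365, and the variance ratio is again 1.37.

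**The case against.** The arithmetic is not in dispute; what it proves about this trial is. The correlations are assumed, and the higher within-period correlation is inferred from timing, not documented. Small gaps cost little (92 to 94% coverage), and 77 to 81% needs gaps of 0.20 to 0.30 that nothing visible supports. This stands as a limit on the size. It does not touch the direction, and a gap of 0.10 already brings coverage to about 89%.

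The block is unstated, and the per-period reading reverses the error. That is true. But that reading discards the within-patient comparison on which Protocol 3.2 rests, and it also gives a wrong interval, so the text needs changing either way.

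The region is joint, so its projection on one endpoint is wider than an ordinary interval. In simulation each projection for the two-week effect covered about 98% at 0.65/0.60, 96 to 97% at 0.70/0.60, 93 to 94% at 0.80/0.60 and 91 to 92% at 0.80/0.50. A reader interested in one endpoint is therefore protected in the moderate cases. The plan, however, promises joint coverage, and that falls.

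The summaries of the treatment difference in SAP 6.1.2 would make a large discrepancy visible, but they do not correct the model's region. Finally, the trial is declared non-confirmatory and no decision threshold is visible. That limits the severity.

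**Conclusion.** The concern holds, as a conditional one. With one block per patient, the specified covariance understates the uncertainty of the two-week effect whenever rw exceeds rb, which is the order this design makes likely. For gaps of 0.05 to 0.20 around rb = 0.60, the SE is 8 to 26% too small and the nominal 95% ellipsoid covers about 92% down to 80%.

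These sizes rest on assumed correlations, equal variances, complete data and 24 completers. Only precision is affected when data are complete and balanced. This should be fixed but does not threaten the trial, given its non-confirmatory status. Confidence is medium, because the true correlations are unknown.

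**What to change.** In Protocol 11.4.2 and SAP 6.1.3, state that the block is the patient and replace compound symmetry with a covariance that separates within-period from between-period correlation. There are two options, and one should be named in advance:

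- random patient and random patient-by-period effects, each with a 2 by 2 (frequency, form) matrix, plus a 2 by 2 residual matrix;
- the direct product of the 2 by 2 endpoint matrix and an unstructured matrix over the four period-weeks.

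The first is easier to support. With complete data, and with the patient-by-period part not truncated at zero, its two-week analysis is that of the period means, whose coverage was checked above. Neither full model was itself simulated, and with about 24 patients convergence is not assured.

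Use Kenward-Roger degrees of freedom. Prespecify the bivariate analysis of period means (22 df with 24 completers) as a check, and as the fallback for the two-week effect. It matches the model only for complete data and gives no weekly effects; for those, the fallback is the same analysis on each week's within-patient difference.

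For the stool index (Protocol 11.5, SAP 6.1.3.3) and the lipid and liver-test models (SAP 7.1.2), state whether one value per period is modelled. A patient-by-period term is needed only if there is more than one.

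The cost is SAP wording and modest programming, with no new data. If the extra correlation is absent, single-endpoint intervals widen by about 4% (t of 2.074 on 22 df against 1.995 on 68 df). The ellipsoid radius grows by about 7% and its area by about 14% (T² of 7.26 against 6.36; √(7.26/6.36) = 1.07). With 30 completers these costs are about 3%, 5% and 11%.
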